At the first visit, patients will receive dermal injections of Restylane[®] followed by IL of triamcinolone acetonide, 10 mg/cc, to approximately 20 sites on one half of the scalp. To assess baseline hair growth, photographs and a modified version of the SALT score will be obtained for each side of the scalp. Degree of scalp atrophy, if any, will be recorded. The scalp will also be examined for erythema, scale, folliculitis. Pull tests will be done.

Restylane[®] 0.02-0.04 mL will be injected to the mid dermis, at the level of the hair bulb, in diseased areas on one half of the scalp. Injections will be placed approximately 1 cm apart and will be repeated for up to 3mL of Restylane[®]. When injections have been completed, the injected areas will be massaged.

Using a fine 1 cc syringe and 30 gauge needle, triamincinolone acetonide 10mg/cc will be administered intralesionally to the entire scalp. Injections will be placed approximately 1 cm apart, injecting 0.1 mL Kenalog-10 into the skin at approximately the level of the hair bulb. Injections will be repeated as needed for up to 4 mL Kenalog-10.

Subjects will remain in clinic 20 minutes following the procedure for recording of adverse reactions.

Visit 2.

Subjects will be asked to return for a second visit 5-6 weeks after injections and the visit 1 procedures will be repeated. The SALT score, alopecia areata half head severity score (AAHHSS score), photography and extent of scalp atrophy will be obtained.

Visit 3.

At the third visit, no injections will be given. The SALT score, AAHHSS score, photography, and extent of scalp atrophy will again be obtained.

Adverse experiences will be recorded at each visit.

Schedule of Study Procedures	Visit 1 (Baseline)	Visit 2 (Weeks 5-6)	Visit 3 (Weeks 11-12)
Signed Informed Consent / Assent and HIPAA Authorization (as required)	X		
Demographic Information	X		
Medical History/Review Medications	X	X	X
Assess Inc/Exc Criteria/Consent	X		
Scalp Physical Examination	X	X	X
Record Concomitant Meds	X	X	X
SALT score	X	X	X
AAHHSS	X	X	X
Photography	X	X	X
Assessment of scalp atrophy	X	X	X
Administer Restylane [®] and triamcinolone acetonide 10 mg/cc	X	X	
Record Adverse Experiences	X	X	X

Inclusion criteria

1. Men and women ages 18 and greater.
2. Alopecia areata diagnosis in the last two years with extensive scalp involvement – between 74% and 99%. . Alopecia areata must involve the left and right hemispheres of the scalp.

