3. Willing to abstain from use of over the counter products and prescription products other than triamcinolone acetonide 10mg/cc which may promote hair growth.
4. Willing to abstain from the use of non-steroidal anti-inflammatory medications, aspirin, St. Johns Wart, and high doses of Vitamin E supplementation.
5. Subjects must be capable of giving informed consent.
6. Willing to adhere to protocol, including scalp examinations and photography.

The gender of the subjects will not determine enrollment. There is no requirement of male to female ratio for this study. The age range of the subjects will be 18 and greater. No specific racial or ethnic restrictions will be present for this study.

Exclusion criteria

1. Allergy or intolerance to Restylane[®] or hyaluronate preparations
2. Allergy or intolerance to triamcinolone acetonide, 10 mg/cc.
3. Underlying disease that might be adversely affected by Restylane[®] or triamcinolone (ex. patients with bleeding disorders).
4. Immunosuppressed patients (history of transplantation, cancer, chemotherapy, splenectomy, HIV).
5. Pregnant or lactating female.
6. Application of topical immunomodulatory or immunosuppressive agent in the preceding 6 weeks.
7. Systemic administration of corticosteroid or other systemic treatment (i.e. prednisone) that has immunomodulatory or other immunosuppressive mechanism of action, in the preceding 8 weeks.
8. Clinical evidence of secondary skin infection (i.e., folliculitis).

9. Other inflammatory or infectious skin disease that might interfere with evaluations during the study.
10. Investigational medications within the past 30 days.
11. Investigational medications within the past 30 days.
12. Patients with susceptibility to keloid formation.
13. Severe allergies manifested by a history of anaphylaxis, or history or presence of multiple severe allergies
14. Patients with allergies to gram positive bacterial proteins
15. Unable to give consent.

During the study period, subjects will be allowed to apply non-medicated shampoos to the scalp.

Statistical Plan

Sample size:

We plan to study 10 subjects. This is a pilot study. The reasoning for sample size selection is to proceed with preliminary studies in a small group. All subjects will be selected based on inclusion and exclusion criteria.

Data Collection:

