Data for this study will be entered into a REDCap database, which uses a MySQL database via a secure web interface with data checks used during data entry to ensure data quality. REDCap includes a complete suite of features to support HIPAA compliance, including a full audit trail, user-based privileges, and integration with the institutional LDAP server. The MySQL database and the web server will both be housed on secure servers operated by the University of Minnesota Academic Health Center's Information Systems group (AHC-IS). The servers are in a physically secure location on campus and are backed up nightly, with the backups stored in accordance with the AHC-IS retention schedule of daily, weekly, and monthly tapes retained for 1 month, 3 months, and 6 months, respectively. Weekly backup tapes are stored offsite. The AHC-IS servers provide a stable, secure, well-maintained, and high-capacity data storage environment, and both REDCap and MySQL are widely-used, powerful, reliable, well-supported systems. Access to the study's data

in REDCap will be restricted to the members of the study team by username and password.

Statistical Analysis:

Data will be analyzed for safety and efficacy of administration of IL triamcinolone acetonide 10 mg/cc and Restylane® in the management of (alopecia areata) AA.

The primary endpoint of evaluating the efficacy of administration of IL triamcinolone acetonide 10 mg/cc and Restylane® in the management of AA is the alopecia areata half head severity score (AAHHSS) comparing week 12 with baseline hair loss. The primary analysis will be a comparison of means of AAHHSS between two treatments on the two sides of AA patients scalp using paired t-tests.

The secondary analysis will examine the mean trend over time for the AAHHSS and SALT score at weeks 0, 6, and 12 using linear mixed models (specifically, using the MIXED procedure of the SAS system, version 9.2) with time after baseline as the fixed effect and using the repeated-measures option of the MIXED procedure.

Safety will be analyzed through determination of the frequency of side effects and/or adverse events recorded during the study.

Supportive analyses will examine the demographic and baseline characteristics of the study sample. Descriptive statistics including either numerically or graphical representations will be used to summarize the data.

Primary Study Endpoints

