To assess the efficacy of IL Restylane® and triamcinolone acetonide 10 mg/cc in the management of AA, baseline hair growth will be recorded via photographs of the scalp and the SALT score and AAHHSS score. Subjects will be asked to return for a second visit at 5-6 weeks for injections. Markers of hair regrowth include the SALT score, the AAHHSS score and photography.

The Severity of Alopecia Tool (SALT) score measures the percentage hair loss at each visit¹⁹. The SALT score is determined through a visual examination of 4 views of the scalp; the percent of terminal hair loss visible in each area is recorded and then aggregated, with a maximum SALT score of 100 corresponding to 100% scalp hair loss¹⁹. In this study, the AAHHSS score will be used to determine hair loss on each half of the scalp when the scalp is divided in the sagittal plane. Each half of the scalp may have a maximum score of 50.

The primary efficacy endpoints are as follows, ranked in order of importance:

1. The AAHHSS will be used to compare hair regrowth on each side of the scalp at 0, 6 and 12 weeks.
2. The SALT score will be used to assess hair regrowth throughout the entire scalp at weeks 0, 6, and 12.

Secondary Study Endpoints

To assess the safety of intralesional Restylane[®] and triamcinolone acetonide 10 mg/cc in the management of alopecia areata scalp examinations will be performed before treatment, immediately after treatment and at 5-6 weeks follow up. Medication side effects and adverse experiences will be recorded. Additionally, subjects will be given a telephone contact number to report side effects anytime after visit 1.

Degree of scalp atrophy will be assessed by the principal investigator and be recorded for comparison across visits.

Medication, Dosing and Dose Rationale

At visit 1, Restylane[®] will be delivered by IL injection into the dermis of the diseased scalp. The minimum and maximum dose of Restylane[®] will be 1mL and 3mL, respectively. The dose of Restylane[®] does not exceed the recommended maximum dose per treatment. Based on clinical U.S. studies on the use of Restylane[®] as a dermal filler for correction of moderate to severe facial wrinkles, the

recommended maximum dose is 6mL. Restylane® will be injected throughout the diseased area by serial puncture. IL injections will be spaced approximately 1cm apart, administering approximately 0.02-0.04mL at each site.

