Once a subject's SALT score is recorded at baseline (Week 0) and at week Z follow up, the percent scalp hair regrowth based on SALT score using the following formula will be determined:

$$\frac{\text{SALT Score at Baseline (Week 0)} - \text{SALT Score at Weeks Z}}{\text{SALT Score at Baseline (Week 0)}} \times 100$$

Where Week Z = the Week for which % hair regrowth from baseline is calculated

50% scalp hair regrowth based on SALT score can be expressed as SALT₅₀
75% scalp hair regrowth based on SALT score can be expressed as SALT₇₅

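### The primary paired t-test does not say whether it compares week-12 AAHHSS or change from baseline between the scalp halves, and neither version handles a baseline left-right difference well

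*Combined protocol and SAP*

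**What the plan says.** In the combined protocol and SAP, the Statistical Analysis section defines the primary endpoint as the "alopecia areata half head severity score (AAHHSS) comparing week 12 with baseline hair loss". The next sentence gives the primary analysis as "a comparison of means of AAHHSS between two treatments on the two sides of AA patients scalp using paired t-tests". Primary Study Endpoints ranks first: "The AAHHSS will be used to compare hair regrowth on each side of the scalp at 0, 6 and 12 weeks". A third scale appears under Determining SALT Score, where "the percent scalp hair regrowth based on SALT score using the following formula will be determined", but only for SALT.

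The baseline data exist. Under Visit 1, "a modified version of the SALT score will be obtained for each side of the scalp", and the Schedule of Study Procedures lists AAHHSS at all three visits. Inclusion criterion 2 requires disease in both hemispheres, but not to an equal extent. The Visit 1 text sends Restylane to one half and gives no rule for choosing it. Triamcinolone goes to both halves.

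The secondary mixed model names time as its fixed effect and has no term for side, so it does not supply a baseline-adjusted comparison of the halves.

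**The concern.** Pairing by patient removes differences between patients. It does not remove a difference that already exists between one patient's two halves. Week-12 score, change from baseline and percent regrowth are three different contrasts, and in the same 10 patients they can differ in size or even in sign. The plan leaves the choice open until the data are in.

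This is the only controlled efficacy comparison in the trial. A baseline imbalance between the Restylane and control halves could appear as a Restylane effect, or hide one.

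**Working it through.** **Plan's own figure.** The sample size is 10, justified only by "The reasoning for sample size selection is to proceed with preliminary studies in a small group". No alpha, power, effect or SD is given, so there is nothing to reproduce. The preliminary SALT change under Clinical Data to Date (mean 20.4, SD 26.5) is a whole-scalp change in another study. It does not give the SD of a between-half difference.

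**Inputs from the documents.** 10 pairs (Sample size); at most 50 AAHHSS points per half (Primary Study Endpoints); 74% to 99% scalp involvement (inclusion criterion 2).

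**Assumptions.** Two-sided alpha 0.05; D0 and D12 (Restylane minus control at baseline and at week 12) each with SD 1; correlation r from 0 to 0.9; mean baseline imbalance b of 0 or 0.5 SD.

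**Step 1: how large can the asymmetry be?** Let whole-scalp loss S be the sum of two half scores, each at most 50. The widest gap has one half at 50 and the other at S - 50, so it is 50 - (S - 50) = 100 - S. That is 26 points at S = 74, 10 at S = 90 and 1 at S = 99. These points assume the 50-point maximum. The SALT worksheet weights for one half sum to 0.36 + 0.40 + 0.24 = 1.00, which implies a maximum of 100 and conflicts with it. Results in SD units are unaffected.

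**Step 2: what each analysis estimates.** Take D12 = delta + r x D0 + e, where delta is the treatment effect and D0 has mean b.

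- Week-12 score: mean delta + r x b; variance 1.
- Change: mean delta - (1 - r) x b; variance 2(1 - r).
- Intercept of D12 on D0: mean delta; large-sample variance 1 - r².

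For example, with b = 0.5, r = 0.7 and delta = 0, the week-12 score is off by 0.7 x 0.5 = 0.35 SD, the change score by -(0.3 x 0.5) = -0.15 SD, and the intercept by 0. The first two errors have opposite signs.

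**Step 3: power and false positives at n = 10.** By the noncentral t distribution, a paired t-test on 10 pairs has 80% power for a difference of 0.996 SD. The table comes from 60,000 simulated trials per cell. Power is for that effect with b = 0; false-positive rates are for delta = 0 and b = 0.5.

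| r | Power %: week 12 / change / adjusted | False positive %: week 12 / change / adjusted |
|---|---|---|
| 0 | 80.1 / 51.2 / 74.1 | 5.0 / 17.3 / 4.9 |
| 0.3 | 79.8 / 65.7 / 77.3 | 6.8 / 13.4 / 4.9 |
| 0.5 | 80.1 / 79.9 / 84.6 | 11.1 / 10.6 / 4.8 |
| 0.7 | 79.9 / 94.8 / 94.6 | 16.7 / 8.5 / 4.9 |
| 0.9 | 80.2 / 100.0 / 99.9 | 24.6 / 6.0 / 4.9 |

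Adjustment costs power when r is 0.3 or lower: 80.1 - 74.1 = 6.0 percentage points at r = 0 and 79.8 - 77.3 = 2.5 at r = 0.3. It gains over week-12 scores from somewhere between r = 0.3 and r = 0.5. A change score overtakes week-12 scores only above r = 0.5, where 2(1 - r) falls below 1.

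A real imbalance also costs the adjusted test some power: with b = 0.5 it has 65.0%, 68.5%, 76.1%, 88.2% and 99.4% down the rows of the table.

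**The case against.** The strongest reply is that the plan already uses baseline. The endpoint sentence immediately before the test refers to week 12 against baseline, and the ranked endpoint speaks of regrowth, so a paired t-test on change is a fair joint reading. On that reading the larger distortions, which belong to week-12 scores, do not arise. When r is high, regression gains no power over change: 94.6% against 94.8% at r = 0.7. The trial also claims no power: "We plan to study 10 subjects. This is a pilot study". Asymmetry is bounded and shrinks towards the upper eligibility limit, and a comparison of the sides at week 0 would make any imbalance visible.

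All of this stands, and it limits the point. A reader might infer that the plan ignores baseline, so that the Restylane estimate is biased and precision is lost. The documents do not support that, for three reasons. The wording allows a change score. A precision gain from adjustment needs r of roughly 0.4 or more, and no r is given. Bias, as opposed to added variance, requires a systematic choice of the treated half; the documents are silent on the rule and do not show such a choice.

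The reply does not settle which variable is tested, and seeing an imbalance is not the same as having a pre-stated way to handle it. If change is meant, it still over-corrects by (1 - r) x b under the model used here.

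**Conclusion.** The point holds as a gap in specification with a better analysis readily available. The test variable is not fixed, and of the three candidates only the baseline-adjusted one kept its error rate near 5% across the r examined with a mean imbalance of 0.5 SD. Week-12 scores gave 5-25% and change 6-17%.

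These sizes are illustrative. They rest on assumed values for alpha, r and the imbalance, on equal SDs, and on a week-12 side difference that is linear in the observed baseline difference. If the imbalance were systematic and baseline scoring error substantial, the intercept could retain some of it. With the treated half chosen at random, chance imbalance adds variance rather than bias.

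The change should be made, but for a 10-patient pilot it is not a fatal flaw. Confidence is medium, because the documents give neither the between-half SD nor the correlation.

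**What to change.** Replace the primary analysis sentence with wording such as: *For each patient, compute the Restylane-minus-control difference in AAHHSS at week 12 (D12) and at baseline (D0). The primary estimate is the intercept of the regression of D12 on D0, that is, the treatment difference at equal baseline, with its 95% confidence interval and a two-sided p-value on (number of complete pairs minus 2) degrees of freedom. A paired t-test on change from baseline is supporting. Absolute AAHHSS points are the primary scale; percent regrowth per half is descriptive.*

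D0 must not be centred at its sample mean, because the intercept would then return the unadjusted week-12 difference. State also how the treated half is chosen, and reconcile the 50-point maximum with the worksheet weights.

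The cost is one paragraph and no new data. With ten complete pairs, degrees of freedom fall from 9 to 8 and the critical t rises from 2.262 to 2.306. The power cost at low r is the one shown in the working.

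### Atrophy and local reactions have no stated comparison between the Restylane half and the triamcinolone-only half; the week 6 AAHHSS side comparison also needs its method named

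*Combined protocol and SAP*

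**What the plan says.** **Design.** Under Methods, Visit 1, Restylane is injected "in diseased areas on one half of the scalp", while triamcinolone "will be administered intralesionally to the entire scalp". Each patient therefore has a combined half and a triamcinolone-only half. The Background gives prevention of steroid atrophy as one of the expected benefits of adding Restylane.

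**Atrophy.** Secondary Study Endpoints states: "Degree of scalp atrophy will be assessed by the principal investigator and be recorded for comparison across visits". Methods, Visit 1 asks for a hair score on each side, then records atrophy and looks for erythema, scale and folliculitis with no side mentioned. The schedule lists atrophy and a scalp examination at all three visits.

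**Safety.** The Statistical Analysis section states: "Safety will be analyzed through determination of the frequency of side effects and/or adverse events recorded during the study".

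**AAHHSS.** The primary endpoint in the Statistical Analysis section is AAHHSS "comparing week 12 with baseline hair loss". The primary analysis is a "comparison of means of AAHHSS between two treatments on the two sides of AA patients scalp using paired t-tests"; that sentence names no week. The secondary analysis covers AAHHSS and SALT at weeks 0, 6 and 12 by linear mixed models, "with time after baseline as the fixed effect and using the repeated-measures option of the MIXED procedure". Primary Study Endpoints ranks this first: "The AAHHSS will be used to compare hair regrowth on each side of the scalp at 0, 6 and 12 weeks".

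**The concern.** Everything that happens to both halves (triamcinolone, natural course, the passage of time) is part of an across-visit change. Only the contrast between halves can remove it. The plan uses that contrast for hair regrowth but states no such use for atrophy or local reactions.

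Two questions are affected. The first is the study's own atrophy hypothesis. The Background lists atrophy at injection sites as a drawback of steroid injection, so some atrophy over the visits would be unsurprising whatever Restylane does. The second is local tolerability. Clinical Data to Date says there is no research on Restylane in the scalp, so which half reacts is basic information from a first pilot.

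The AAHHSS question at week 6 is similar but smaller. The Background puts regrowth after steroid injection at 4 to 8 weeks, so a time trend at week 6 is expected even if Restylane adds nothing.

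**Working it through.** The plan has no figure of its own to reproduce here. The sample of 10 is given as a pilot number without alpha, power, effect size or SD. The check is a comparison of the texts, with illustrations whose inputs are marked as assumed.

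**1. Which contrast isolates Restylane.** Let N be natural course, S the steroid effect and R the Restylane effect on change from baseline, taken as additive.

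- Combined half: N + S + R
- Triamcinolone-only half: N + S
- Between-half difference: (N + S + R) - (N + S) = R
- Across-visit change averaged over halves: N + S + R/2

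R cannot be recovered from the last line without knowing N + S, which only the other half supplies. If S differs between halves, the between-half difference is R plus that difference in S.

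**2. Atrophy (assumed counts).** No patient has atrophy at baseline; 4 of 10 have it at week 12.

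| Where the 4 patients have it | Across visits, by patient | Combined half | Triamcinolone-only half | Combined minus triamcinolone-only |
|---|---|---|---|---|
| Triamcinolone-only half | 0% to 40% | 0/10 | 4/10 | -40 points |
| Both halves | 0% to 40% | 4/10 | 4/10 | 0 |
| Combined half | 0% to 40% | 4/10 | 0/10 | +40 points |

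The across-visit result is identical in a case that favours Restylane, a neutral case and a case against it.

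**3. What 10 patients can give.**

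- Graded score, paired mean difference: 95% half-width = t(0.975, 9 df)/√10 = 2.262/3.162 = 0.715 SD of the difference.
- Yes/no atrophy, 4 discordant pairs all one way: exact two-sided McNemar p = 2 × 0.5⁴ = 0.125. Five pairs give 0.0625; six give 0.031. At least six, all in one direction, are needed for p < 0.05.
- For the same 4 versus 0, the Tango score interval is 1.1 to 68.7 points in size. It excludes zero although the exact p is 0.125, so an approximate interval can look more decisive than the data are.
- No local reactions on 10 combined halves: exact 95% upper limit = 1 - 0.025^(1/10) = 0.308.

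**4. AAHHSS at week 6 (assumed means at weeks 0, 6, 12).** Triamcinolone-only half 42, 38, 34; combined half 42, 32, 24.

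- Time-only model on both halves: week 6, (38 + 32)/2 - 42 = -7; week 12, (34 + 24)/2 - 42 = -13.
- Side differences in change: week 6, (32 - 42) - (38 - 42) = -6; week 12, (24 - 42) - (34 - 42) = -10.
- Swap the two halves: the time effects stay at -7 and -13, and the side differences become +6 and +10.

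Fitted to each half separately, the model gives two trends that can be subtracted by hand, but no valid interval for the difference, because the pairing is lost.

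**5. Why the weeks need ranking.** Two unadjusted tests at 0.05, at weeks 6 and 12, have a familywise error of 1 - 0.95² = 0.0975 if independent, and less if positively correlated.

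**The case against.** **The side comparison at week 6 is already there.** Primary Study Endpoints commits to comparing sides at 0, 6 and 12 weeks, and the Statistical Analysis section gives paired t-tests, in the plural, for comparing sides. Reading the two together is natural. The mixed model is offered for the mean trend over time, so lacking a side term is no error in that role. This largely stands: a reader might infer that the plan omits a week 6 side comparison, and the documents do not support that. What is missing is a sentence tying the t-tests to visits.

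**Silence on side is not pooling.** A reader might infer that events will be pooled, or that atrophy will not be recorded by half. The text says neither, and the forms are not in the documents. That stands too. It remains true that no between-half analysis is stated. The general sentence on descriptive statistics follows the one on demographic and baseline characteristics and mentions neither halves nor atrophy.

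**The protocol's evidence on triamcinolone is thin.** A reader might infer that its data show steroid-induced atrophy. They do not: the Background gives no frequency, and the earlier triamcinolone study reports no atrophy result. Its mean SALT change of 20.4 is a 24-week before-after figure without a control group. The point therefore rests on the design and the stated hypothesis.

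**The between-half contrast is itself imperfect.** No random or blinded allocation of side is described, nor any vehicle injection on the other half. The principal investigator grades atrophy. Medication, Dosing and Dose Rationale ties triamcinolone volume to lesion size, so volume may differ by half. All of this stands and should be reported as limits. The across-visit comparison lacks even this imperfect control.

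**It is a pilot of 10.** True, which is why the request is for description and not for a powered test.

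**Conclusion.** The main point holds with high confidence. As written, the plan states no analysis that can address the atrophy hypothesis, or the local tolerability of Restylane, against the within-patient control. The week 6 point is a clarification, held with moderate confidence.

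No sample size or power figure changes, and the primary between-half AAHHSS comparison is unaffected; a reader should not infer that it is invalid. The size is one of interpretation: in the illustration, one across-visit result fits between-half differences from -40 to +40 points. This assumes roughly additive effects and similar steroid exposure in the two halves; the counts and means are invented.

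Nor should a reader infer that the added analysis would settle the hypothesis. With 10 patients, a 4 versus 0 split still gives an exact p of 0.125. The change is a cheap improvement that should be made before enrolment, because a side not recorded at the visit may not be recoverable later.

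**What to change.** **Recording.** At all three visits, record degree of atrophy and local reactions (erythema, scale, folliculitis, injection-site events) separately for each half.

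**Atrophy and safety analysis.** Report the within-patient between-half difference in change in atrophy from baseline at weeks 6 and 12. Use an interval suited to 10 pairs (signed-rank for a graded score, exact for yes/no) and label it descriptive. Tabulate local events by half and systemic events by patient. State the limits: no random or blinded side allocation described, no vehicle injection on the other half described, grading by the principal investigator, and triamcinolone volume that may differ by half.

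**AAHHSS.** State that the paired between-half comparison of change from baseline is primary at week 12 and secondary at week 6, each with the side difference and 95% CI. Alternatively, add side and side-by-visit terms to the AAHHSS mixed model, with within-patient correlation across halves and visits, and report the same differences. Keep the time-only model for SALT, which is a whole-scalp score.

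**Cost.** A few sentences in the statistical plan and a side field if the forms lack one. Visits and examinations stay the same. The downside is slightly more recording and analysis, for estimates that will be imprecise.
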